4.6 Retention and Follow Up

Intervention visits: For participants who are actively taking part in the CHP intervention or Education condition their assigned clinician or educator will be charged with scheduling sessions and rescheduling missed sessions. Participants will be reminded 1 day prior to their scheduled sessions by a study staff.

Research visits: Study staff will maintain strong and consistent relationships with study participants, and should contact study participants by text, phone, and/or email at minimum once per every follow up assessment to assure follow up scheduling and attendance. During this phone outreach, site study staff can verify existing contact information. Study staff should take note of participants who are less stable in terms of contact information i.e. Phone number/e-mail address, and devote outreach efforts toward these participants strategically.

***NOTE: Due to COVID-19, all follow-up assessments completed after 3/15/2020 were conducted remotely via Zoom and online survey administration via Qualtrics.

4.7 Specimen Collection

At baseline we test for Urethral and Rectal Gonorrhea & Chlamydia presence. The testing method for Urethral G&C will involve the participant urinating in a sterile urine collection cup and then send it for testing to Sunrise medical Laboratory. For Rectal detection we will provide the participant with an anal swab collection kit, and send the specimen for STI detection to Sunrise Medical Laboratory. In addition to the STI detection we will collect participant's fingernails and potentially toenails in case the sample is not enough, to test illicit drug use in the last 6 months, this 5-Panel drug assay will be conducted by USDTL Laboratory. HIV testing is performed at session 3

with both members of the couple present and will be performed utilizing HIV 4th Generation Rapid Test Determine Ab/Ag. Reporting to any required Departments of Health will occur using standard protocols.

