 5.2 Intervention Training and Supervision11

6.0 SAFETY MONITORING PLAN12

 6.1 Data and Safety Monitoring Board.....12

Abbreviations:

TRB – Transmission Risk Behavior
MSM – Men who have Sex with Men
YMSM – Young Men who have Sex with Men
TLFB – Time Line Follow Back
STI – Sexual Transmitted Infection
BL – Baseline appointment
FU – Follow Up appointment

STUDY ABSTRACT

DESIGN: This study utilizes qualitative methods during a formative phase to inform intervention development. Subsequently a small randomized controlled trial is utilized in Phase 2 to evaluate the feasibility, acceptability, and preliminary efficacy of the new intervention relative to an attention-matched education control condition.

SAMPLE SIZE: In Phase 2 we will recruit a sample of 50 couples (n = 100 individuals). At least one member of the couple must be a YMSM between the ages of 18 and 29; report recent (past 30 days) drug use; and recent (past 30 day) Transmission Risk Behavior (TRB).

POPULATION: Partnered MSM aged 18-29 who are in a primary relationship with another man for at least 3 months, who also uses some kind of illicit drug, and also had some TRB in the last 30 days with a casual partner or with a non-monogamous serodiscordant partner. In addition all participants will have to be able to communicate in English.

STRATIFICATION: Participants will be randomized at baseline to receive their first CHP or Education session directly following their baseline appointment. The study will employ a stratified randomization procedure using Qualtrics.

DATA COLLECTION: Participants have the options to first complete a brief CASI at home before or during their BL appointment. Regardless, they will then complete another survey at their BL appointment along with a TLFB, STI testing (Gonorrhea & Chlamydia Urethral and Rectal), and Drug testing. During session 3, participants will complete a CHTC session that involves Rapid HIV testing for couples. For 1m FU participants will complete an at home Qualtrics survey. At 3M FU participants will complete a Qualtrics survey, a TLFB and a Fingernail specimen collection for drug use.

[figure not shown]
Study Procedure Guide (SPG)

Finally, at 6M FU participants will complete a Qualtrics survey, a TLFB and Specimen collection to test drug use on fingernail sample and Gonorrhea & Chlamydia for STI testing (Urethral and Rectal).

OBJECTIVES

- 1) Develop content to address PrEP uptake/adherence and integrate biological testing

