- 2) Evaluate the efficacy, feasibility, and acceptability of CHP at 3- and 6-month follow-up.

STUDY DESIGN:

Original Study Timeline:

Month	Year 1					Year 2		Year 3	
	1-2	3-4	5-8	9	10-12	13-18	19-24	25-30	31-36
Planned activity									
Phase I: intervention development									
Startup	■								
Interviews with partnered YMSM (n = 20)		■							
Qualitative data analysis			■						
Intervention development and staff training				■					
Phase II: enrollment									
Enrollment (n = 50 couples; 100 individuals)						■	■	■	■
Follow up data collection						■	■	■	■
Data analysis									
Dissemination of qualitative findings						■			
Intervention outcome analyses									■

STUDY POPULATION

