4.3 Randomization Process/Systems

Participants will be randomized at the end of their baseline assessment into one of two control conditions: 1) delivery of the 3 session CHP intervention or 2) delivery of a 3 education sessions. Each participant's condition will be tracked in the access tracking database maintained by the Research Coordinator.

The study will employ a stratified randomization procedure for each interventionist using Qualtrics. Randomization will be stratified on:

1. Age discrepancy Question: is the couples age difference (3 years or less/ longer than 3 years)
2. Relationship Length Question: is the couple's relationship length (2 years or less/longer than 2 years)
3. Racial makeup question: is the couples racial makeup (both partners identify as white and non-Hispanic/one or both partners identify as nonwhite or Hispanic)

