4.4 Schedule of Assessments

Intervention or education sessions will occur approximately once per week for two weeks beginning one week after completion of the baseline assessment and session 1. There is a 6 week window (45 days) for intervention or education completion, i.e. opportunities to complete all three sessions must be provided before the 1 month online follow up survey is sent out.

Participants will complete the first follow-up assessment online 1 month after baseline (1M FU). For those who have completed all sessions by day 30 post BL, they will be sent their 1 month follow up survey. For those who have yet to complete all 3 sessions they will be given until day 45 post baseline until their session window closes and they must be sent their 1 month follow up survey. The 1 month follow up survey will close 60 days post baseline. Follow up assessment windows for 3 month and 6 month follow ups will be programmed to open on day 90 and day 180 respectively and will remain open for 30 days.

Component	Screening	Baseline	Session 1	Session 2	Session 3	Booster	1-Month Follow-Up	3-Month Follow-Up	6-Month Follow-Up
Informed Consent		X							
CASI		X					X	X	X
HIV Testing					X				
STI Testing (G&C)		X							X
Fingernail Drug Test		X						X	X
Randomization		X							
Randomized Condition Session			X	X	X	X			
TLFB		X						X	X
Assessment of Intervention feedback					X				
Assessment of Intervention feedback (If not completed or captured in session 3)							X		

Refer to “Study Design” for a visual representation of the schedule of assessments.

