4.7.1 Key Biological Testing

- **5-panel fingernail drug assay.** Though studies have consistently supported the validity of self-reported drug use data⁹⁴⁻⁹⁷, when individuals are informed that their self-reported behavior will be validated through biological measurement, they are more likely to report their behaviors accurately⁹⁸. Drug testing will be completed using the Nail Testing Panel from the United States Drug Testing Lab[®] (USDTL). Participants will clip 100 mg of nail (approximately 10 clippings of 2mm each). Clippings will be weighed on a jeweler's scale to ensure the collection of an adequate sample. Clippings are transferred to a foil packet, stored at room temperature, and shipped to USDTL via secure envelope. Results are available in 4 to 5 business days⁵².
- **Urethral STIs.** Urethral STIs (chlamydia and gonorrhea) are being tested with laboratory assay from Sunrise Medical Laboratory, which detects both chlamydia and gonorrhea precisely. Participants will collect a urine sample and then place the specimen tube into a clear plastic biohazard bag. Specimens will be sent to Sunrise Medical Laboratory for processing. Sunrise Medical Laboratory will provide us with test results and will report positive results to the NYC DOH complying with New York City Health Department Reporting Requirements 101.
- **Rectal STIs.** Participants will also perform testing for rectal chlamydia and gonorrhea using a test kit from Sunrise Medical Laboratory. The swab is approximately the size of a Q-tip and is grasped between the thumb and forefinger about an inch from the base. The swab is inserted until the fingers touch the anus, and then it is rotated as it is removed. Swabs are stored in a specimen tube and a clear plastic biohazard bag. Specimens will be sent to Sunrise Medical Laboratory for processing. Sunrise Medical Laboratory will provide us with test results and will report positive results to the NYC DOH complying with New York City Health Department Reporting Requirements 101.
- **Disclosure of Urethral and Rectal STI Results:** Test results will be conveyed to participants through a secure Qualtrics-based interface along with a list of local resources. Per New York City's Health Code Article 11, the lab Sunrise Medical Laboratories will report positive results directly to the DOHMH

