- **HIV testing.** HIV testing will be conducted in the context of couples' HIV testing conducted in session 3 of both conditions. Testing will be performed using the Alere Determine Ab/Ag Testing Kit[®]. An RA trained in CHTC will utilize a lancet to gather a sample of blood from the participant's finger. This blood is then collected with a capillary tube and placed on the designated area of the test strip, and then a drop of chase buffer is added to the testing area to culture. Test results are available in 20 minutes and delivered to participants immediately

during the couples HIV testing and counselling session. For additional information on HIV confirmatory testing and reporting see Attachments.

***NOTE: Due to COVID-19, collection of biological specimen data was suspended on 3/15/2020. All follow-up assessments completed after that date were conducted remotely via Zoom and online survey administration via Qualtrics.

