Couples Health Project: Data Analysis Plan

Development of a couples-based intervention to reduce drug use and enhance sexual health among partnered emerging adults.

NCT# 03386110 LAST UPDATED: 6/1/2021

Analytic plan

A series of bivariate analyses conducted using the generalized estimating equations function within SPSS (version 25) evaluated the success of randomization and the presence of differential attrition. In models evaluating randomization, condition (MI-intervention versus control) served as the sole predictor of baseline characteristics. Analogous models evaluating differential attrition predicted baseline characteristics from a dichotomous variable indicating whether or not a participant completed a specific follow-up.

Multi-level models calculated in Mplus (version 8.2; 48) evaluated primary hypothesized direct treatment effects. These models controlled for the nesting of participants within couples and permitted the specification of logistic and count (Poisson or negative-binomial) distributions as appropriate. Full-information maximum likelihood estimation was utilized to retain all cases in a true intent-to-treat paradigm. For each outcome, 3- and 6-month values were predicted by treatment condition.

The hypothesis that baseline frequency of drug use or CAS with casual partners may moderate the effects of treatment was evaluated using the Actor-Partner Interdependence Model (APIM) framework (49). Models incorporated participants' own baseline report of the outcome (actor scores) as well as their partners' report (partner scores) at Level 1. Interactions among actor and partner baseline scores and treatment condition were also included at Level 1. This included the 3-way interaction term as well as all possible 2-way interactions. A natural log transformation was used to address skew in these predictor variables. For models involving count-distributed outcomes, effect size was calculated using procedures outlined by Larsen and Merlo (50) for the calculation of an Interval Odds Ratio.

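### Does the six-month reach of the fingernail assay call for a SAP rule that limits nail comparisons to the 6-month sample?

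*Protocol*

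**What the plan says.** Protocol section 4.7 (Specimen Collection) says that nails are collected "to test illicit drug use in the last 6 months, this 5-Panel drug assay will be conducted by USDTL Laboratory". The sentence belongs to a paragraph that opens with baseline testing. The schedule in section 4.4 lists the same nail test at baseline, 3 months and 6 months, and the Study Abstract confirms the middle one: "At 3M FU participants will complete a Qualtrics survey, a TLFB and a Fingernail specimen collection for drug use".

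Time zero comes from section 4.3: "Participants will be randomized at the end of their baseline assessment into one of two control conditions". Section 4.4 says that the 3- and 6-month windows "will be programmed to open on day 90 and day 180 respectively and will remain open for 30 days", so the visits fall on days 90–120 and 180–210.

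On purpose, section 4.7.1 supports the assay with the argument that "when individuals are informed that their self-reported behavior will be validated through biological measurement, they are more likely to report their behaviors accurately". The COVID-19 note at the end of that section records that "collection of biological specimen data was suspended on 3/15/2020".

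The second objective is to "Evaluate the efficacy, feasibility, and acceptability of CHP at 3- and 6-month follow-up". The SAP says: "For each outcome, 3- and 6-month values were predicted by treatment condition". It does not name the nail result as an outcome. Its moderation paragraph works with each man's own and his partner's reports.

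**The concern.** A test that looks back six months, taken three months after randomisation, mixes use before and after treatment assignment. The mixing matters in this population. Section 3.1 requires at least one partner to report recent drug use, and the 3-month look-back reaches at least 60 days before baseline. It therefore covers the whole 30-day eligibility period if screening took place within 30 days of baseline.

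Two errors could follow. If 3-month nail results were compared between arms, a real reduction in use could look smaller than it is, which is unwelcome in a trial of 50 couples. If a 3-month positive were set against a TLFB report of stopping, an honest report could be taken for under-reporting.

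Such uses are foreseeable. Nails are collected beside the TLFB at all three visits, the objective is efficacy at 3 and 6 months, and the SAP's model sentence covers every outcome without defining the list. The SAP also states no baseline covariate for the direct-effect models. Neither document mentions the overlap.

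**Working it through.** The documents state no overlap figure, so there is none to reproduce.

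**Inputs.** Look-back L is six months (section 4.7), taken as 180 to 183 days. Visit day t is 90–120 or 180–210 (section 4.4). Day 0 is baseline (section 4.3). Two assumptions are needed: the look-back applies equally to follow-up clippings, and there is no lag between use and detection.

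**Share of the look-back before randomisation** = max(0, L − t)/L.

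| Visit day | L = 180 | L = 183 |
|---|---|---|
| 90 | 90/180 = 50.0% | 93/183 = 50.8% |
| 120 | 60/180 = 33.3% | 63/183 = 34.4% |
| 180 | 0% | 3/183 = 1.6% |
| 210 | 0% | 0% |

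With L = 184 the day-180 share is 4/184 = 2.2%.

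**Sensitivity to the assumptions.** A shorter look-back reduces the overlap: L = 120 gives 30/120 = 25% at day 90 and none at day 120, and L = 90 gives none at either. A lag increases it. With an assumed 30-day lag and L = 180, a day-180 sample covers days −30 to 150, so 30/180 = 16.7% precedes randomisation. The 6-month sample is nearly free of overlap only if the lag is negligible, and the documents give no lag.

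**What the overlap would do to a contrast.** These are shares of calendar time, not of effect.

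- Binary result, treatment acting only by making some men stop: observed difference = true difference × (1 − q), where q is the share of those stoppers still positive from earlier use. An illustrative 30-point difference shows as 30 points at q = 0, 15 at q = 0.5 and 0 at q = 1. The documents do not narrow q.
- Quantitative result with even weighting over the look-back: the retained effect is 1 − share, from 1 − 0.508 = 0.492 to 1 − 0.333 = 0.667. The sample needed rises by 1/0.667² = 2.25 to 1/0.492² = 4.13 times.

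In both cases the contrast shrinks towards zero. Use before randomisation is balanced between arms in expectation, so neither arm is favoured.

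**What a 6-month-only rule would cost.** Counting back from 3/15/2020, the last baselines that allow a 6-month sample are 9/17/2019 (visit on day 180) or 8/18/2019 (day 210). For a 3-month sample they are 12/16/2019 (day 90) or 11/16/2019 (day 120). The band of baselines with a 3-month sample only runs from 60 days (9/17 to 11/16) to 120 days (8/18 to 12/16). If that band lay within enrolment, and enrolment was even over 18 to 24 months (assumed), the count is 50 × 60/(24 × 30.44) = 4.1 to 50 × 120/(18 × 30.44) = 11.0 couples.

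**The case for a change.** The best case for a change is that it is cheap and the misuse is easy to foresee. Two or three SAP sentences could rest any nail comparison on the baseline-adjusted 6-month sample, report the 3-month result descriptively, and let a 3-month positive contradict a TLFB report only where the baseline nail was negative for that drug. Under the even-weighting calculation, the 6-month sample is the more informative one unless it is smaller than about 24% to 44% of the 3-month sample (0.492² to 0.667²). Some loss to the suspension would not overturn that preference.

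The arithmetic stands, and so does the preference for 6 months on sensitivity grounds. Three things count against the rule.

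- It governs an analysis that neither document plans. The SAP sentence on outcomes does not make the nail result one of them, and nothing in the planned models of reported behaviour depends on the nail look-back.
- Restricting the comparison to 6 months is a trade-off, not a correction. It discards 3-month data to avoid a loss of sensitivity that a statement of the look-back would already convey. The 6-month sample is not a pure post-treatment measure either: with L = 180 to 183, about 8% to 26% of its look-back precedes the day-45 close of the session window (15/180 to 48/183).
- The baseline-negative rule can itself go wrong. If detection lags use, drug taken shortly before baseline could be missed at baseline and appear at 3 months. An honest report of stopping would then be counted as contradicted.

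Timing also weakens the case. The SAP is dated 6/1/2021 and written in the past tense, after specimen collection had been suspended. A rule added now could not be a commitment made before the data were collected.

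**Conclusion.** No change is called for. About 33% to 51% of the 3-month nail look-back precedes randomisation, against about 0% to 2% at 6 months, given a 180- to 184-day look-back, the same assay at follow-up and no detection lag. That limits how a 3-month nail result can be read, but it does not affect any analysis the plan sets out. Following the SAP as written gives no wrong answer because of it, and the assay's stated role in supporting honest self-report is intact.

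Should anyone later compare nail results between arms, ordinary practice covers the point: adjust for the baseline nail result, show both visits with the look-back stated, and read the 3-month contrast as the less sensitive one. By the same reasoning, a 3-month positive alone does not refute a TLFB report of stopping. The size of any attenuation cannot be fixed from the documents, which give neither the panel's drugs, nor whether results are binary or quantitative, nor the lag to detection. The figure of 4 to 11 couples rests on the assumed enrolment pattern.

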4.7.1 Key Biological Testing

- **5-panel fingernail drug assay.** Though studies have consistently supported the validity of self-reported drug use data⁹⁴⁻⁹⁷, when individuals are informed that their self-reported behavior will be validated through biological measurement, they are more likely to report their behaviors accurately⁹⁸. Drug testing will be completed using the Nail Testing Panel from the United States Drug Testing Lab[®] (USDTL). Participants will clip 100 mg of nail (approximately 10 clippings of 2mm each). Clippings will be weighed on a jeweler's scale to ensure the collection of an adequate sample. Clippings are transferred to a foil packet, stored at room temperature, and shipped to USDTL via secure envelope. Results are available in 4 to 5 business days⁵².
- **Urethral STIs.** Urethral STIs (chlamydia and gonorrhea) are being tested with laboratory assay from Sunrise Medical Laboratory, which detects both chlamydia and gonorrhea precisely. Participants will collect a urine sample and then place the specimen tube into a clear plastic biohazard bag. Specimens will be sent to Sunrise Medical Laboratory for processing. Sunrise Medical Laboratory will provide us with test results and will report positive results to the NYC DOH complying with New York City Health Department Reporting Requirements 101.
- **Rectal STIs.** Participants will also perform testing for rectal chlamydia and gonorrhea using a test kit from Sunrise Medical Laboratory. The swab is approximately the size of a Q-tip and is grasped between the thumb and forefinger about an inch from the base. The swab is inserted until the fingers touch the anus, and then it is rotated as it is removed. Swabs are stored in a specimen tube and a clear plastic biohazard bag. Specimens will be sent to Sunrise Medical Laboratory for processing. Sunrise Medical Laboratory will provide us with test results and will report positive results to the NYC DOH complying with New York City Health Department Reporting Requirements 101.
- **Disclosure of Urethral and Rectal STI Results:** Test results will be conveyed to participants through a secure Qualtrics-based interface along with a list of local resources. Per New York City's Health Code Article 11, the lab Sunrise Medical Laboratories will report positive results directly to the DOHMH
- **HIV testing.** HIV testing will be conducted in the context of couples' HIV testing conducted in session 3 of both conditions. Testing will be performed using the Alere Determine Ab/Ag Testing Kit[®]. An RA trained in CHTC will utilize a lancet to gather a sample of blood from the participant's finger. This blood is then collected with a capillary tube and placed on the designated area of the test strip, and then a drop of chase buffer is added to the testing area to culture. Test results are available in 20 minutes and delivered to participants immediately

during the couples HIV testing and counselling session. For additional information on HIV confirmatory testing and reporting see Attachments.

***NOTE: Due to COVID-19, collection of biological specimen data was suspended on 3/15/2020. All follow-up assessments completed after that date were conducted remotely via Zoom and online survey administration via Qualtrics.

